### Intervention Procedure Description:

At the time of the intervention procedure, a 22 or 20-g angiocatheter will be placed in the participant's hand/arm for peripheral intravenous access for conscious sedation during the procedure. The patient will be positioned supine on a fluoroscopy table with a positioning device under the patient's knee to create 30-40 degrees knee flexion and hemodynamic monitors will be placed including NIBP, pulse oximeter and nasal cannula oxygen at 1-4 L/min. The knee will be prepped with chloroprep for 1 minute and draped in a sterile fashion. A grounding pad will be placed on the patient's contralateral thigh and connected to the RF generator which will be turned on but will not be in the patient's view. Regardless of group assignment, midazolam 0.5-1 mg IV aliquots and/or fentanyl 25-50 mcg IV aliquots will be given as needed to provide

appropriate anxiolysis and analgesia for needle placement and manipulation for the duration of the procedure. NM policies and procedures for conscious sedation will be followed.

For active CRFA, three targets for ablation\* will be identified with an AP view of the knee:

- 1.) Superior lateral genicular nerve
- 2.) Superior medial genicular nerve
- 3) Inferior medial genicular nerve
- \*=locations are based on anatomic studies and Choi et al publication

The skin and deep subcutaneous tissues overlying these target sites will each will be anesthetized using 5-10 mL of 1% lidocaine. An 18 G C-RFA cannulas (Cooled Radiofrequency Kit, Halyard Health), (75 or 100mm) will be placed through the skin to be optimally positioned via an anterior approach at the anatomic location of each of the 3 targets using AP and lateral fluoroscopic imaging. The disposable RF electrode that is supplied with RF kit will be placed into the cannula and attached to the RF generator; sensory and motor testing will be performed to confirm safe and appropriate placement. Following this confirmation, 2 cc of 2% lidocaine will be injected at each of these three sites. After 2 minutes, the targets will be lesioned at 60 degrees Celsius for 2 minutes 30 seconds. Following this, all needles will be removed and Band-Aids placed on the needle placement sites. Participants will be transferred to a recovery area and monitored in a reclining position for at least 30 minutes to allow sedation to wear off.

For sham control, the three targets for ablation will be identified in a similar manner. The skin overlying the target sites identified with image guidance will each be anesthetized using 5-10 mL of 1% lidocaine. A 3.5 or 5 inch 22 gauge Whitacre needle will be placed through the skin to be optimally positioned at the anatomic location of each of the 3 targets using AP and lateral fluoroscopic imaging. Following this placement confirmation, 2 cc of 2% lidocaine will be injected at each of these sites. Non-disposable radiofrequency electrodes will be placed through these needles and attached to a RF generator. The same auditory and visual experience of RF lesioning will be mimicked in the sham group as presented in the treatment group (see above). After 2 minutes and 30 seconds, the electrodes and needles will be removed and Band-Aids placed on the needle placement sites. Participants will be transferred to a recovery area and monitored in a reclining position for at least 30 minutes to allow sedation to wear off.

## Economic Burden to Subjects: None

Subject Reimbursement: Participants will receive \$100 after completing the 3 month follow up and another \$50 after completing the 6 month follow up. Participants will be required to provide their name, telephone number, and mailing address. The telephone number will be used to contact the participants at study intervals and to verify correct mailing address prior to sending payment. Participants will be told there is a 4 to 6 week processing time. They will be asked to sign an accountability log to document payment.

## Statistical Analyses:

Baseline characteristics (e.g., sociodemographic variables, primary and secondary outcomes) will be compared between treatment groups using t-tests or chi-square tests for categorical variables. We will conduct intent-to-treat (ITT) analyses for all primary and secondary outcomes

using a series of generalized mixed-effects regressions. All statistical tests will be two-sided with significance set at  $p\leq.05$ . SAS statistical software version 9.2 (SAS Institute Inc., Cary, NC, USA) will be used for statistical analyses.

In preliminary analysis, the distributional aspects of the variables under consideration will be examined through descriptive statistics. These statistics will include measures of location (mean, median, quartiles) and measures of dispersion (range, standard deviation, variance) for continuous variables and frequencies of the levels of categorical variables. These measures will also assist with a data cleaning/screening procedure to eliminate any possible copying, handling, recording or measurement errors. In addition to the features described above, the dependence of outcome measures will need to be properly accounted for in the data analysis as measures will be made at multiple times for the same participant. Consequently, these observations tend to be correlated and require statistical techniques that can properly account for the correlation in order to draw valid inference. Our general approach for analyzing these multiple types of data in this trial will be the Generalized Linear Mixed-Effect Models (GLMM).

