### Secondary Outcomes include:

- a) Visual Analog Scale for pain: (0 (no pain) to 10 (unbearable pain) scale; at rest, mobilization/ weight bearing.
- b) Knee Society Scale (clinician); WOMAC (patient)
- c) Time to Physical therapy milestones:
  - a. Active SLR
  - b. Time until patient can get out of bed
  - c. Time until patient able to ambulate < 100 feet
  - d. Time until patient able to ambulate around room > 100 feet
  - e. Time until patient is able to climb stairs (quantify specifics, how many steps are considered appropriate?)
- d) Patient Global Perception of Change (GPC)

e) Patient Satisfaction (Likert Scale)

f) Hospital Anxiety and Depression Score (HADS)

- e) SF 12 Questionnaire
- f) McGill Pain Questionnaire
- g) Inpatient length of Stay (LOS; days) and Physical Therapy "clearance for discharge" (days)
- h) Complications of the injection procedure
- i) Medication related adverse effects

A total of 60 patients will be randomized. Participants will complete assessments at these time points:

- 1) Baseline: immediately before the CRFA intervention,
- 2) Immediately prior to surgery (Day of Surgery)
- 3) 48 hours after the surgery procedure
- 4) 1, 3 and 6 months following TKR surgery.

A member of the research team will administer and collect the questionnaires. It will take about 5-10 minutes to complete the questionnaires. The research member will visit the patient at 48 hours to administer the questionnaire and collect data points. It will take approximately 5-10 minutes to complete the questionnaire. In addition, a member of the research team will contact the patient by phone or at scheduled surgical visits at 1 month, 3 months and 6 months.

A member of the research team will look in POWERCHART for physical therapy milestones. Other data points such as medication use, length of stay, time for PT clearance, surgical duration will be recorded. Data collection will be placed on a excel sheet and stored in a pass word protected computer in the department of anesthesiology. Paper data sheets will be placed in a binder and stored in a locked filing cabinet in a locked office located in the department of anesthesiology.

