#### Participants

Inclusion criteria include:

- 1) Adults 30 to 80 years old
- 2) OA of the knee scheduled to undergo their first unilateral knee joint replacement
- 3) Willingness to undergo fluoroscopy-guided C-RFA or sham treatment.

Exclusion criteria include:

- 1) Conditions that preclude C-RFA or sham intervention (e.g. pregnancy, severe cardiac/pulmonary compromise; acute illness/infection; coagulopathy or bleeding disorder; allergic reactions/contraindications to a local anesthetic).
- 2) Prior TKR on either knee
- 3) Inability to write, speak or read in English
- 4) Patient refusal

Recruitment

Site(s) where study will be performed: Department of Anesthesiology, [name] Department of Orthopedic Surgery, [name] Patients who schedule a primary unilateral TKR with their orthopedic surgeon at NM will be asked to participate in the study by authorized research personnel. They will be screened to determine candidacy for the study; if they meet eligibility criteria, they will read and sign an informed consent form to participate. Each participant will be scheduled to see [name] in the Pain Medicine Center for the intervention procedure. They will be asked to be NPO for this visit and arrange a driver to accompany them home. This procedure will be performed 2-4 weeks prior to their planned knee surgery. The research assistant will calculate Morphine Equivalents (ME) of all analgesic medications including opiates, anti-inflammatories and membrane stabilizers.

Each participant will complete the following written outcome measures prior to the intervention: It will take approximately 10 minutes to complete the questionnaires.\* VAS pain score WOMAC questionnaire SF12 questionnaire Hospital Anxiety and Depression Inventory questionnaire McGill Questionnaire

Following the intervention procedure the following data points will be recorded: VAS pain score PGIC Questionnaire Patient satisfaction

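### The primary 48-hour comparison names no baseline covariate, although usable pre-procedure data are collected; adjusting for one would be a cheap gain in precision only

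*Combined protocol and SAP*

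**What the plan says.** All references are to the combined protocol and SAP.

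- **Statistical Analyses.** Baseline data have one stated use: "Baseline characteristics (e.g., sociodemographic variables, primary and secondary outcomes) will be compared between treatment groups using t-tests or chi-square tests". Primary and secondary outcomes are then to be analysed by intention to treat "using a series of generalized mixed-effects regressions", because "measures will be made at multiple times for the same participant". No model terms are listed.
- **Statistical Power.** The trial is sized on a two-sided Mann-Whitney test, which has no covariate.
- **4.0 Data Analysis.** The primary outcome is a between-group difference in MQS III score at 48 hours, with no mention of adjustment.
- **4.2 Interpretation of Anticipated Results.** The groups are compared by t tests (described as paired) or Wilcoxon rank sum tests, with no baseline term.
- **Participants, Recruitment text.** "Each participant will complete the following written outcome measures prior to the intervention"; VAS is on the list that follows. The research assistant will also "calculate Morphine Equivalents (ME) of all analgesic medications including opiates, anti-inflammatories and membrane stabilizers", but no time point is given and this item is not on that list.
- **Assessment times under Secondary Outcomes.** The first is "Baseline: immediately before the CRFA intervention" and the second is "Immediately prior to surgery (Day of Surgery"). Of the intervention, the Recruitment text says: "This procedure will be performed 2-4 weeks prior to their planned knee surgery".

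**The concern.** A baseline variable that predicts the outcome can remove part of the between-patient variation from the treatment comparison without recruiting anyone. Here the plan uses baseline values for significance tests between randomized groups. Those tests add nothing to the precision of the treatment estimate and do not replace a prespecified covariate.

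The trial has little slack: power .81 at 28 per group, and 30 recruited per group. A narrower interval would be useful. If the plan stays silent, a covariate could also be chosen after the data are seen, and the choice could fall on a day-of-surgery value, which is measured 2 to 4 weeks after the procedure and may already reflect its effect.

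**Working it through.** **Inputs (Statistical Power).** Difference 15 ME per 24 hours; SD 19 ME; control mean 47 ME; 28 per group; two-sided alpha 0.05; stated power .81 by Mann-Whitney. The correlation r between covariate and outcome is not in the documents, so it is an assumption and is shown over a range.

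**Step 1: reproduce the plan's figure.** Under normality the Mann-Whitney test has asymptotic relative efficiency 3/π = 0.955 against the t test. The effective size is 28 × 0.955 = 26.7 per group, and t-based power at that size is 0.809. Simulation of the Mann-Whitney test itself gives 0.80. The stated .81 holds.

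**Step 2: unadjusted comparison on the raw scale.**
- SE = 19 × √(2/28) = 5.078, df = 54.
- Noncentrality = 15/5.078 = 2.954, giving power 0.827.
- 95% CI half-width = 2.005 × 5.078 = 10.18 ME.

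**Step 3: add one baseline covariate.** SE = 19 × √(1 − r²) × √((2/28) × (53/52)), df = 53. The factor 53/52 allows for chance imbalance in the covariate. The half-width is 2.006 × SE.

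| r (assumed) | SE | 15/SE | Power | Half-width (ME) |
|---|---|---|---|---|
| none (unadjusted) | 5.078 | 2.954 | 0.827 | 10.2 |
| 0 | 5.127 | 2.926 | 0.819 | 10.3 |
| 0.2 | 5.023 | 2.986 | 0.834 | 10.1 |
| 0.3 | 4.890 | 3.067 | 0.853 | 9.8 |
| 0.5 | 4.440 | 3.379 | 0.913 | 8.9 |

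Break-even is r = 0.14. The worst case, r = 0, costs about 0.7 power points (0.8267 to 0.8193). At r = 0.5 the half-width falls by about 13% (8.90/10.18 = 0.87).

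**Step 4: type I error.** In simulation at r = 0.5 with no treatment effect, the rejection rate was 0.047 unadjusted and 0.049 adjusted. Adjustment does not change the error rate.

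**Step 5: rank version, to stay near the Mann-Whitney sizing.** Simulated power for regression of ranked outcome on treatment and ranked covariate is 0.803, 0.816, 0.833 and 0.891 at r = 0, 0.2, 0.3 and 0.5, against about 0.80 for Mann-Whitney. The gain is similar, but the ME half-widths do not apply to ranks.

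**Step 6: which covariate is available.** VAS is documented as collected before the procedure. For analgesic use the evidence is indirect: the ME calculation appears in the Recruitment text without a time point, while Statistical Analyses counts the primary outcome among baseline characteristics. Together these suggest a pre-procedure value but do not establish it.

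**The case against.** **Not an error.** The unadjusted comparison is unbiased under 1:1 randomization, and the sizing does not rely on adjustment. This stands, and it sets the severity: a reader might infer that the planned comparison is invalid or underpowered, and the documents support neither.

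**The gain rests on an undocumented r.** This also stands. The covariate would be measured 2 to 4 weeks before surgery. The ME measure pools several drug classes, whereas General Design and Procedures defines the outcome as post-operative opiate requirement. VAS is a different construct from analgesic use. Nothing in the documents supports a high r, and below about 0.2 the gain is negligible.

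**The mixed model may already use baseline.** A repeated-measures model that includes the Baseline visit could do so. The text does not commit to this: it names no terms and does not say whether baseline is a response time or a covariate. So it would be too strong to say that the plan ignores baseline; the role of baseline is unspecified.

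**Change scores.** From the word describing the t tests in section 4.2, or from the repeated-measures language, a reader might infer that change from baseline is the primary analysis and that power would suffer. The documents do not support that. No section defines a change-from-baseline primary outcome; 4.0 states a between-group difference at 48 hours, and 4.2 says its tests compare the two treatment groups.

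**Larger conflicts come first.** The primary outcome is opiate requirement in General Design and Procedures, ME per 24 hours in Statistical Power, and MQS III in 4.0. The primary method is a mixed model, a Mann-Whitney test, or t/Wilcoxon tests, depending on the section. This stands: a covariate cannot be specified properly until both are settled.

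**Conclusion.** The point holds as a minor improvement in precision. No section names a baseline covariate for the primary 48-hour comparison, and at least one usable pre-procedure measure is collected. The possible effect runs from a loss of about 0.7 power points at r = 0 to a gain of about 8.6 points at r = 0.5 (0.827 to 0.913), with a modest 2.6 points at r = 0.3 (0.827 to 0.853).

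These figures assume normal data, 28 analysed per group, SD 19, and ME per 24 hours as the primary scale. If MQS III is the primary outcome, the ME half-widths do not carry over, and the power figures would need that scale's own difference and SD.

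**What to change.** 1. First reconcile the primary outcome scale (General Design and Procedures and Statistical Power against 4.0) and the primary method (Statistical Analyses, Statistical Power, 4.2).
2. Then prespecify, before unblinding, a regression of the 48-hour outcome on treatment plus one pre-procedure covariate. Use pre-procedure analgesic use on the same scale as the outcome if its timing before the procedure is confirmed; otherwise use pre-procedure VAS. Do not select the covariate by baseline p-values.
3. Fix the analysis scale in advance: raw if an interval in outcome units is wanted, or ranks of outcome and covariate to stay close to the Mann-Whitney sizing.
4. State that day-of-surgery values are not covariates for this comparison, because they come after treatment.
5. If the mixed model is kept for the primary outcome, state whether baseline enters as a covariate or as a response time.

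**Cost.** After step 1, which is needed anyway, one or two sentences and a check of when ME is recorded. VAS needs no new data; analgesic use needs none if its timing is confirmed and it can be expressed on the chosen scale. The analysis spends one degree of freedom, and the sample size is unchanged.

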### Randomization and Masking Procedures (Treatment vs Control; T vs C)

A computer-generated 1:1 block randomization scheme will be used to assign participants to receive either a CRFA *or* a sham procedure (wherein no RF energy is delivered after needle placement, and only local anesthetic is delivered). Randomization will be performed by the proceduralist immediately before the injection procedure by opening an opaque envelope to reveal the participant number and group assignment printed on an index card. Participants, surgeons and all other study personnel, including those who will perform follow-up evaluations, will be blinded to group assignment. One board certified, fellowship trained anesthesiologist ([name]) with 16 years of injection experience will perform all injections. [name] will not be involved in the collection of any primary or secondary data outcome.

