### 4.2 Interpretation of Anticipated Results:

## Statistical analysis

Means and standard deviations of participant demographic data, as well as mEQ, VAS, and other outcome scores will be calculated. Two tailed paired t tests will be used for parametric data; Wilcoxon rank sum tests will be used for non-parametric data in order to compare differences in outcome measures between the two treatment groups.

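### Baseline balance between randomised arms is to be tested at p ≤ .05, and the plan does not say whether the secondary scales will be adjusted for their own pre-procedure scores

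*Combined protocol and SAP*

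**What the plan says.** All references are to the combined protocol and SAP.

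- **Baseline tests.** Statistical Analyses: "Baseline characteristics (e.g., sociodemographic variables, primary and secondary outcomes) will be compared between treatment groups using t-tests or chi-square tests for categorical variables". The same section adds: "All statistical tests will be two-sided with significance set at" p ≤ .05, with no exception for the baseline tests.
- **Allocation.** Randomization and Masking Procedures: "A computer-generated 1:1 block randomization scheme will be used to assign participants".
- **Baseline data.** Under Participants: "Each participant will complete the following written outcome measures prior to the intervention". The list is "VAS pain score WOMAC questionnaire SF12 questionnaire Hospital Anxiety and Depression Inventory questionnaire McGill Questionnaire". The same section adds analgesic use: "The research assistant will calculate Morphine Equivalents (ME) of all analgesic medications including opiates, anti-inflammatories and membrane stabilizers". The list of assessment times opens with "Baseline: immediately before the CRFA intervention".
- **Outcome analysis.** Statistical Analyses makes generalised linear mixed models the general approach, because patients are measured repeatedly. It names no covariate and no contrast, and does not say whether the baseline score is a response, a covariate or neither.
- **Comparisons.** Section 4.0 lists the secondary comparisons as between groups at 48 hours and at 1, 3 and 6 months. Section 4.2 names paired t tests and Wilcoxon rank sum tests "in order to compare differences in outcome measures between the two treatment groups", with no covariate.

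**The concern.** There are two linked problems.

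First, a significance test of baseline balance asks whether chance produced the difference. After sound randomisation the answer is known to be yes, so a small p-value can only mislead, for example by suggesting that randomisation failed. A large p-value does not show that the arms are alike, because the test is insensitive with 30 patients per arm.

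Second, the useful role for a pre-procedure score is as a covariate in the analysis of the same scale at follow-up, and the plan does not assign it that role. Pain scores are one of the two outcomes in the research question (section 1.1), the other being analgesic use, and the trial has only 60 patients. At stake are the precision of the pain and questionnaire comparisons and an adjustment choice left open until the data have been seen.

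**Working it through.** **The plan's own figure.** The plan gives no figure for baseline imbalance. Its sample size does reproduce. Using the Mann-Whitney efficiency 3/π, the effective n is 28 × 3/π = 26.7 per group. A two-sided t-test with difference 15, SD 19 and alpha .05 then has power 0.8085, against the stated .81. The calculations below use the recruited 30 per arm.

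**Step 1: false alarms.** For k independent tests at .05 under sound randomisation, the chance of at least one significant result is 1 − 0.95^k. The documents name five scales plus morphine equivalents. Sociodemographic variables are mentioned but not counted.

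| k | At least one p ≤ .05 |
|---|---|
| 5 | 22.6% |
| 6 | 26.5% |
| 10 | 40.1% |
| 13 | 48.7% |
| 14 | 51.2% |

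Scores on one patient are likely to be correlated. With an assumed common correlation of .5, simulation gives 20.7% for k = 6, 28.5% for k = 10 and 34.8% for k = 14.

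**Step 2: what a non-significant test can miss.** The smallest flagged difference in SD units is t(.975, 58) × √(2/30) = 2.002 × 0.2582 = 0.517. An observed imbalance just under 0.52 SD passes as no difference.

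**Step 3: value of the baseline score as a covariate.** Let r be the correlation between a scale's baseline and follow-up values (assumed; the documents give none). Adjustment multiplies the variance of the treatment difference by about 1 − r², which is equivalent to 30/(1 − r²) patients per arm. The power column assumes a 0.5 SD effect, 30 per arm and a normal approximation; without adjustment it is 49%.

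| r | 1 − r² | Variance cut | 30 per arm act like | Power |
|---|---|---|---|---|
| .3 | 0.91 | 9% | 33 | 53% |
| .5 | 0.75 | 25% | 40 | 61% |
| .7 | 0.51 | 49% | 59 | 77% |

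**Step 4: does a repeated-measures model settle this by itself?** No; it depends on the contrast. Suppose baseline is one of the repeated responses and the arm means at baseline are left free. With complete data, the between-arm difference at a follow-up visit is then still the unadjusted one (variance factor 1). With equal variances, the difference in change from baseline has factor 2(1 − r) = 1.4, 1.0 and 0.6 at r = .3, .5 and .7. Both exceed 1 − r². The gain in Step 3 needs baseline as a covariate, or a model that constrains the baseline means to be equal.

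**The case against.** The strongest reply is that the plan is silent on baseline adjustment and does not rule it out. Baseline is the first listed assessment time, the mixed model is justified by repeated measurement, and a paired t test in section 4.2 may hint at a before/after use. A list of times at which arms are contrasted does not settle what enters the model. This stands: a reader might infer that the secondary analyses ignore baseline, but the documents show only that its role is unstated. Step 4 shows why the silence still matters.

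Other stronger readings also fail:

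- **About half of sound trials would show a false imbalance.** That needs 13 or 14 independent tests. The documents name six variables and give no total, and pain, function and mood scores are unlikely to be independent.
- **Adjustment will be chosen by the baseline p-value.** No passage attaches any action to a significant baseline test. Even if adjustment were chosen that way, 100,000 simulated null trials with 30 per arm give type I error of about .047, .044 and .035 at r = .3, .5 and .7, which errs on the conservative side.
- **The unadjusted comparison is biased.** It is not. Its standard error already allows for chance imbalance, and an observed difference of 0.5 SD or more on a given scale arises in only about 5.8% of sound trials.

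It is also fair to say that baseline p-values in a table change no treatment estimate.

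**Conclusion.** The point holds as a gap in prespecification and a loss of precision. The planned baseline tests are uninformative: about 21% to 26% of sound trials would show at least one significant result on the six named variables, and more if sociodemographic variables or subscales add tests. Differences below about 0.52 SD would go unflagged. Unless baseline enters the models, the analyses of VAS, WOMAC, SF-12, HADS and McGill forgo a variance reduction of about 9%, 25% or 49%.

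These sizes rest on assumed correlations: up to .5 among baseline variables, and .3 to .7 between baseline and follow-up. No bias or type I inflation is shown. The point does not reach outcomes without a listed pre-procedure value, such as change ratings, satisfaction, physical therapy milestones and length of stay, nor the primary 48-hour comparison.

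**What to change.** 1. In Statistical Analyses, replace the baseline t-tests and chi-square tests with a descriptive table by arm, using the summaries that the section already plans. State that no baseline p-value will be used to judge randomisation or to choose covariates.
2. For each secondary scale measured before the procedure (VAS, WOMAC, SF-12, HADS, McGill), take only post-baseline values as the response. Enter that scale's own pre-procedure score as a prespecified fixed covariate, whatever the observed imbalance. A constrained-baseline model is an acceptable alternative. Keeping baseline as a response while adding it as a covariate would use it twice.
3. Align section 4.2 with this, so that one adjusted analysis is stated for these scales.

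The cost is a few sentences of wording, one degree of freedom per model and a simple rule for missing baseline forms. No new data, visits or patients are needed.

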To date, few publications have demonstrated the use of RFA for knee pain from OA. Choi et al used conventional RFA of the articular nerves in the knee in elderly patients with chronic knee pain from OA in a double blind randomized controlled trial published in 2011. RFA at three nerve locations was performed with image guidance and each lesion was performed at 70 degrees C for 90 seconds with a 22 gauge cannula. Needle placements were at the region connecting the shaft of the femur to the bilateral epicondyles (superior lateral and superior medial genicular nerves) and the shaft of the tibia meeting the medial epicondyle (inferior genicular nerve). Patients who underwent RFA reported at least a 50% decrease in pain scores at one and three months following the procedure, whereas the sham control group had no demonstrable change in pain at these time points. Oxford knee disability scores and patient satisfaction scores were also significantly improved in the RFA group but unchanged in the control group. No adverse events were reported in the 38 patients enrolled in the study. In a single case report, conventional RFA of periarticular nerves in a patient with chronic knee pain following TKR was described with favorable clinical results and drastically improved pain control, but the RFA was performed remote to the time of the TKR for the indication of chronic pain, not to treat perioperativ pain in the immediate postoperative and rehabilitative periods.

Thus, although RFA has been used in patients with chronic knee pain from OA and in one case treating chronic pain many months following knee replacement, C-RFA has not been used in the perioperative management of pain in patients undergoing total knee joint replacement surgery.

The aim of this study is to determine if patients undergoing unilateral total knee replacement obtain any pain relieving benefits from C-RFA of the articular sensory nerve supply prior to surgery, as compared to sham controls who receive only local anesthetic injections of these same nerves without the benefit of ablation treatment.

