### Risks/Benefits:

The risks of C-RFA of the articular sensory branches of the knee are minimal. Sensory and motor testing of the target structure prior to lesioning reduces the risk of any neurologic injury and the motor nerves are not located at the planned lesion sites. Bleeding or infection can occur with any needle intervention.

Summary of Recruitment:

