### 4.0 Data Analysis:

Primary outcome:

• Between-group difference in analgesic use (MQS III score) at 48 hours.

Secondary outcomes: Between groups at 48 hours, 1, 3, 6 months in:

- 1. Visual Analog Scale for pain (at rest, with mobilization or weight bearing)
- 2. Knee Society Scale (clinician); WOMAC (patient)
- 4. Physical therapy milestones
  - a. Time to active SLR
  - b. Time until patient can get out of bed
  - c. Time until patient able to ambulate < 100 feet
  - d. Time until patient able to ambulate around room > 100 feet

e. Time until patient is able to climb stairs (quantify specifics, how many steps are considered appropriate?)

- 5. Patient Global Perception of Change (GPC)
- 6. Patient Satisfaction (Likert scale)
- 6. Hospital Anxiety and Depression Score (HADI)
- 7. SF12
- 8. McGill Pain Questionnaire

9. Inpatient length of Stay (LOS; days) and Physical Therapy "clearance for discharge" (days)

- 10. Complications of the injection procedure
- 11. Medication related adverse events (i.e. sedation, nausea, pruritus, delirium)

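### Injection complications fall under the blanket mixed-model rule, which gives no finite odds ratio or usable Wald interval if an arm has no events; an exact comparison should be named instead

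*Combined protocol and SAP*

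**What the plan says.** The Statistical Analyses section sets one rule: "We will conduct intent-to-treat (ITT) analyses for all primary and secondary outcomes" "using a series of generalized mixed-effects regressions". It adds: "Our general approach for analyzing these multiple types of data in this trial will be the Generalized Linear Mixed-Effect Models (GLMM"). The reason given is that each participant is measured at several times. The section names no link function, no test statistic and no fallback for sparse events. Chi-square is mentioned only for comparing baseline characteristics. The level is two-sided 0.05.

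Section 4.0 lists among the secondary outcomes "Complications of the injection procedure" (item 10) and "Medication related adverse events (i.e. sedation, nausea, pruritus, delirium") (item 11). Both also appear in the secondary outcome list under General Design and Procedures.

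On how often complications may occur, section 2.1 says of the cited trial of conventional RFA: "No adverse events were reported in the 38 patients enrolled in the study". Risks/Benefits says: "The risks of C-RFA of the articular sensory branches of the knee are minimal". Neither gives an expected rate. The paragraph on use of only one exposure rules out repeat injections.

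Section 4.2 gives a second set of between-group tests, t tests (described as paired) and Wilcoxon rank-sum. It does not mention event proportions and is not reconciled with the mixed-model rule.

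**The concern.** The mixed model is justified by repeated measurement. Whether a patient had a complication of a single injection is one binary value, so a random intercept has nothing to account for.

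The harder problem is sparse data. If one arm has no events, the maximum-likelihood log odds ratio for arm is infinite. Software then either warns of non-convergence or stops at a large arbitrary estimate with a far larger standard error. The Wald p-value, if that is what is read off, tends to 1 however many events the other arm has.

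Section 2.1 states that C-RFA has not been used for perioperative pain in knee replacement, and section 2.2 looks ahead to adding it to the treatment algorithm. The complication count will be read in that light, and the planned model may yield no usable effect estimate or interval for it.

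**Working it through.** **Inputs.** 60 patients randomized 1:1, so 30 per arm (General Design and Procedures; Randomization and Masking Procedures). Two-sided alpha 0.05 (Statistical Analyses). Event rates are not in the documents, so a range is assumed below.

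**The plan's own figure.** The documents give no figure for complications. The one sample-size figure, 28 per group with power 0.81 for the primary outcome, does reproduce: a two-sample calculation with difference 15 and SD 19 needs 26 per group, and 26 / 0.955 (the Mann-Whitney efficiency for normal data, 3/π) = 27.2, rounded up to 28. It has no bearing on harms.

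**Step 1: how likely is an arm with no events?** With the same true rate p in both arms, P(0 of 30) = (1 − p)^30, and P(at least one arm has none) = 1 − [1 − (1 − p)^30]².

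| Assumed rate p | P(0 of 30) | P(at least one arm with none) |
|---|---|---|
| 1% | 0.740 | 0.93 |
| 2% | 0.545 | 0.79 |
| 3% | 0.401 | 0.64 |
| 5% | 0.215 | 0.38 |
| 10% | 0.042 | 0.08 |

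**Step 2: what does the model return?** For 7/30 versus 0/30, an ordinary logistic fit gives a log odds ratio of about 22.4 with SE about 14,500, so z = 22.4 / 14,500 = 0.0015 and Wald p = 0.999. Fisher's exact two-sided p is 2 × C(30,7) / C(60,7) = 2 × 2,035,800 / 386,206,920 = 0.0105.

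The mixed model behaves in the same way. For 6/30 versus 0/30, a random-intercept logit fitted by quadrature gave Wald p between 0.92 and 0.999, depending on the convergence tolerance and on whether 1 or 4 records per patient were used; at the tightest tolerance with 4 records no standard error could be computed.

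**Step 3: do other tests fail too?** For 6/30 versus 0/30: Fisher 0.024, chi-square 0.0098, likelihood ratio 0.0027, rank-sum on event indicators 0.011. They do not. The failure belongs to the estimate, its standard error and anything Wald-based.

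**Step 4: when do Fisher and Wald reach different verdicts?** Fisher p with 30 per arm:

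| Events | Fisher p |
|---|---|
| 3 v 0 | 0.237 |
| 4 v 0 | 0.112 |
| 5 v 0 | 0.052 |
| 6 v 0 | 0.024 |
| 7 v 0 | 0.011 |

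The verdicts part only from 6 versus 0 upward. By the binomial distribution, the chance of 6 or more events in an arm of 30 is about 0.00003 at a 2% rate, 0.003 at 5% and 0.07 at 10%.

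**Step 5: what would an exact interval say?** If no C-RFA patient has a complication, the two-sided 95% Clopper-Pearson upper limit is 1 − 0.025^(1/30) = 0.116, or 11.6%.

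**The case against.** The strongest reply has four parts.

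First, a p-value near 1 needs a logit link, no penalty and a Wald test, and the plan names none of these. This stands. A reader might infer that the planned analysis must fail or must report no difference. The documents do not support that: a likelihood-ratio test on the same model gives 0.0027 at 6 versus 0. Nor does the plan choose that test, so the result depends on a decision left open.

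Second, the rank-sum test in section 4.2 would detect the excess if applied to event indicators. This also stands as arithmetic, but section 4.2 does not assign it to events, and the two sections are not reconciled.

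Third, if complications are as rare as section 2.1 and Risks/Benefits suggest, 6 or more in one arm is very unlikely, so Wald and Fisher would nearly always agree on non-significance. This stands and limits the consequence. The percentages in Step 1 are chances of an empty arm, not of a wrong conclusion. The missing estimate and interval remain a defect at any count with an empty arm.

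Fourth, a reader might extend the point to all medication-related events. The rarity evidence concerns the RFA procedure only. No rates are given for sedation, nausea, pruritus or delirium, and some of these may be common enough for the mixed model to work. Nor do the documents make complications a main product of the trial: the research question and primary outcome concern pain and analgesic use.

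**Conclusion.** The point holds for injection complications, as a minor one. The blanket rule assigns a once-per-patient, probably rare binary outcome to a model that has no finite odds ratio or usable Wald interval when an arm has no events. An empty arm has a chance of 38% to 93% at assumed common rates of 5% down to 1%. A Wald test, if used, would then give p near 1 even at 7 versus 0.

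This rests on three assumptions: a logit link without penalization, one yes/no value per patient, and event rates that the documents do not state. Only a secondary safety analysis is affected. The primary outcome is not. The 11.6% limit follows from having 30 patients and would not be narrowed by a change of test. It is a figure to report, and it does not show the pre-trial description of risk to be wrong.

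**What to change.** In Statistical Analyses and section 4.0, take complications of the injection procedure out of the mixed-model rule. State that the number of patients with at least one complication will be reported by arm, that arms will be compared by Fisher's exact test with an exact or score confidence interval for the risk difference, and that the Clopper-Pearson limit will be given for the C-RFA arm.

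Use the same method for any medication-related event with a zero or very sparse cell. Common medication-related events can stay in the mixed model. State that section 4.2 does not govern these events, or bring it into line.

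The cost is a sentence or two in the plan, with no new data or patients. Fisher's test is slightly conservative: 5 versus 0 gives p = 0.052. A non-significant result with 30 per arm should therefore not be read as showing safety, and the interval should be reported beside the p-value.
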